3.2 EXCLUSION CRITERIA

- Patients undergoing revision surgery, any operations for trauma, infection, tumor
- Patients with general metabolic diseases such as rheumatoid arthritis, diabetes, chronic heart and renal diseases.

4.0 SUBJECT REGISTRATION

The subjects will be recruited by the PI, co-investigators, or authorized study staff at the orthopaedic surgery clinic or prior to their ACDF surgery in the pre-operative hold area in. The study will be reviewed with the subjects and they will be consented by the PI, co-investigator, or other authorized study staff.

Each collaborating site will be involved in subject recruitment, consent, and all data collection for any patients that are enrolled in the study at each respective site.

5.0 STUDY DESIGN & METHODS

We intend to prospectively evaluate 85 patients as part of a single blind, randomized controlled study. Subjects would be randomized to group I (control group, no steroid), group II (10 mg of intraoperative intravenous decadron with gel foam sponge placed on cervical plate), or group III (40mg of triamcinolone on gel foam sponge dabbed on the anterior cervical plate). Subjects will be blinded to the treatment arm. Randomization will take place on the day of surgery. 85 envelopes will be sealed, 25 of which will contain a document specifying “control”, “iv steroids”, or “steroid sponge”. The 75 envelopes will then be shuffled to create a random assortment. The circulating nurse in the OR will at random choose one envelop prior to the start of the operative procedure. This will in turn specify the treatment group for each patient.

There is no standard of care regarding the use of IV or local steroids in the setting of ACDF. Currently, the use of either IV or local steroids is at the discretion of the attending surgeon. To my knowledge, there are several spine surgeons at our institution that currently use no steroid, and others who use a combination of IV and/or local steroids.

The primary outcome measure is the incidence of dysphagia as measured by Eating Assessment Tool (EAT-10) and the Bazaz score. The patients will prospectively fill out these surveys preoperatively, post-operative day 1, week 2, week 6, month 3, month 6, and 1 year as a measure of dysphagia. The standard of care is to see patients in the office at 2 weeks, 6 weeks, 3 months, 6 months, and 1 year after surgery, and therefore, no extra visits will be necessary for this study. X-rays will be taken at 6 weeks, 3

months, and 12 months post-op, which is the current standard of care. No additional x-rays will be obtained.

A secondary outcome measure will be the incidence of dysphonia, as measured by the Voice Handicap Index (VHI-10), as well as other validated outcome measures (NDI, VAS, EQ-5D). The questionnaires will take approximately 20 minutes to complete and will be administered in the hospital, during the post-operative clinic visits with the surgeon, or over the phone. The surgeons will also listen to the patient's voice at these different time points and comment on dysphonia as being absent, mild, moderate, or severe.

Additionally, a chart review will be performed from 1/1/2013 to 12/30/2016 from NMH Medical records (PRIMES, Cerner PowerChart) and NMFF Medical Records (EpicCare, IDX/GE Centricity) to obtain the following data: Complications such as infection, post-operative hematoma, airway compromise, and recurrent laryngeal nerve palsy. All data collected from chart review will be de-identified and noted on the Data Collection Form. Each subject will be assigned a study number and all data will be linked to that number using the Coded Identifier List. The PI will identify which charts will be reviewed. The chart review will be performed by the PI, co-investigators, or authorized study coordinator.

There are potential physical risks from being in this study. The use of steroids may have an adverse effect on wound healing and/or transiently elevate blood sugar. There have been no documented wound complications from using either IV or local steroids in the setting of ACDF. Furthermore, we purposely excluded patients with a history of diabetes or other endocrine disorder in an attempt to minimize this potential side-effect or complication. Another possible risk related with participation in this study is the loss of privacy. To reduce these risks, all of the information collected will be de-identified and stored in a password protected file on a password protected computer. Additionally, some of the questions asked in the surveys may be upsetting, or the subject may feel uncomfortable answering them. If the subject does not wish to answer a question, they may skip it and go to the next question.

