A SINGLE BLIND, PROSPECTIVE, RANDOMIZED CONTROLLED TRIAL ON THE EFFECT OF LOCAL STEROID APPLICATION VERSUS INTRAVENOUS STEROIDS ON DYSPHAGIA FOLLOWING ANTERIOR CERVICAL DISECTION AND FUSION

PRINCIPAL INVESTIGATOR: [name], FACS
[name]
[name]
[contact]
[contact]
[contact]

SUB-INVESTIGATORS: [name]
Northwestern University

[name]
Northwestern University

[name], MD
University of Wisconsin-Madison

[name], MD
OrthoCarolina Research Institute

PARTICIPATING SITES: Northwestern Memorial Faculty Foundation
(NMFF)
[name]
[name]
[contact]

Northwestern University (NU)
[name]
[name]

OrthoCarolina Research Institute
[name]
[name]

University of Wisconsin-Madison

FUNDING AGENCY: Cervical Spine Research Society (CSRS)

Synopsis

Title	A single blind, prospective, randomized controlled trial on the effect of local steroid application versus intravenous steroids on dysphagia following anterior cervical discectomy and fusion (ACDF)
Short Title	Effect of local application vs. IV steroids on dysphagia after ACDF
Protocol Date	12/14/2015
Study Duration	2 years
Study Center(s)	Northwestern Memorial Faculty Foundation (NMFF), Northwestern University (NU), University of Wisconsin-Madison, OrthoCarolina Research Institute
Objectives	Local application of steroids in ACDF surgery will lead to decreased incidence of dysphagia compared to intravenous steroids or a control group
Number of Subjects	85 (randomized to group I (control group), group II (10 mg of intraoperative intravenous decadron), or group III (40mg of triamcinolone placed on cervical plate), i.e. 25 per group.
Diagnosis and Main Inclusion Criteria	Patients undergoing ACDF (single or multi-level) for the treatment of radiculopathy or myelopathy by Drs. [name], [name], and [name].

TABLE OF CONTENTS

Synopsis	2
1.0 Introduction	4
2.0 Study Objectives	4,5
3.0 Selection of Subjects	5
3.1 Inclusion Criteria.....	5
3.2 Exclusion Criteria.....	5
4.0 Subject Registration	5
5.0 Study Design & Methods	5,6
6.0 Statistical Plan	6
7.0 Data Collection & Record Keeping	6
8.0 References	7
Appendices	8

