6.0 STATISTICAL PLAN

We will use T score or ANOVA to compare EAT-10 scores, VHI scores, and EQ-5D, and Chi square for subjective findings. The P value will be set at 0.05.

A power analysis was performed to determine the sample size needed. Based on previous studies evaluating the EAT-10 in normal patients and those with dysphasia the analysis concluded: with total sample size 85 (Group I: 25, Group II: 25, Group III: 25) and estimated standard deviation of EAT-10 as 12.7, **power = 0.92**

Drs. [name], [name], and [name], perform approximately 6 ACDFs a month. This would allow us to collect our proposed sample size in approximately 12-14 months.

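### Treatment is assigned by a free pick from one shuffled pool of envelopes with no stated order, log or custodian, so a redraw could not be detected and balance within site is not ensured

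*Combined protocol and SAP*

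**What the plan says.** Section 5.0 (Study Design & Methods) gives the whole procedure. Timing: "Randomization will take place on the day of surgery". Preparation: "85 envelopes will be sealed, 25 of which will contain a document specifying" one of the three arms, followed by "The 75 envelopes will then be shuffled to create a random assortment". Assignment: "The circulating nurse in the OR will at random choose one envelop prior to the start of the operative procedure". The same section describes the trial as single blind and names only the subjects as blinded. On practice outside the trial it says that "the use of either IV or local steroids is at the discretion of the attending surgeon", and that colleagues at the institution differ in what they use.

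The synopsis lists four centers: "Northwestern Memorial Faculty Foundation (NMFF), Northwestern University (NU), University of Wisconsin-Madison, OrthoCarolina Research Institute". Two of them share the Northwestern name. Section 4.0 (Subject Registration) adds that "Each collaborating site will be involved in subject recruitment, consent, and all data collection" for its own patients. Section 6.0 (Statistical Plan) names ANOVA and related tests without a site term.

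The documents do not mention numbered or opaque envelopes, a required opening order, a log, a custodian outside the operating team, envelope sets by site, blocking or stratification.

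**The concern.** Allocation concealment should make it impossible to change an assignment after seeing it, or at least make any change visible. With a free pick there is no required next envelope. Someone who opens one and dislikes the arm can return it and take another, and nothing in the stated procedure would show it. The pick takes place in the operating room, among staff who are not said to be blinded, in a setting where steroid preferences are known to differ. If redraws depended on prognosis, the arms would differ before treatment, and no later analysis could fully repair that.

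The second question is practical. One shuffled pool cannot be in the operating rooms of separate institutions at once. Someone must divide it or duplicate it, and the plan does not say how. If it is divided by hand, the arm mix at each site is left to chance.

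**Working it through.** **1. The plan's own count.** Three arms of 25 give 3 x 25 = 75. Section 5.0 seals 85 envelopes and shuffles 75; Section 6.0 repeats the mismatch ("with total sample size 85 (Group I: 25, Group II: 25, Group III: 25"). The figure of 85 is not reproduced: 85 - 75 = 10 envelopes have no stated content. The appendix forms run to 75.

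**2. What a redraw could do to one assignment.** Take the chance of a preferred arm as 1/3 per pick, with the envelope returned each time.
- One pick: 33%.
- One redraw allowed: 1 - (2/3)^2 = 5/9 = 56%.
- Two redraws allowed: 1 - (2/3)^3 = 19/27 = 70%.

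**3. What redraws could do to the comparison (illustration).** Half the patients are high risk (+0.8 SD) and half low risk (-0.8 SD); 0.8 SD is the mean of each half of a normal distribution. A fraction q of high-risk control draws moves evenly to the two steroid arms.
- Control mean = -0.8q/(2 - q).
- Each steroid-arm mean = +0.8q/(4 + q).
- Bias, steroid minus control = 0.8[q/(2 - q) + q/(4 + q)] SD.

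The SD of 12.7 comes from Section 6.0. The values of q and of the correlation r between foreseeable prognosis and EAT-10 outcome are assumptions.

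| q | Bias in SD | r = 1 (x 12.7) | r = 0.5 | r = 0.3 |
|---|---|---|---|---|
| 0.1 | 0.06 | 0.8 | 0.4 | 0.2 |
| 0.2 | 0.13 | 1.6 | 0.8 | 0.5 |
| 0.3 | 0.20 | 2.5 | 1.3 | 0.75 |

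The r = 1 column is a maximum: it treats the whole SD of EAT-10 as foreseeable before surgery and sends every redraw the same way. For scale, the plan gives no target difference. Its power of 0.92 with SD 12.7, 25 per arm and two-sided 0.05 implies about 12.1 points in a two-arm comparison.

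**4. Balance within site.** A site receiving k envelopes from a 25/25/25 pool gets arm counts (a, b, c) with probability C(25,a) C(25,b) C(25,c) / C(75,k). Summing over all counts whose largest and smallest differ by 5 or more gives:
- k = 15: 27%.
- k = 19: 30%.
- k = 25: 36%.

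The chance that at least one site has such a gap is 65% for a 25/25/25 split, 59% for 45/15/15 and 71% for 19/19/19/18. The documents give no site sizes, so every k and every split is assumed. If all 75 envelopes are used, the overall totals are still 25 per arm.

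**5. Does imbalance within site bias the result?** With three assumed sites of 25, site means 0.5 SD apart and an unadjusted ANOVA, 20,000 simulated trials gave a type I error of 0.051 and a mean site-driven arm difference of zero. It does not.

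**The case against.** The strongest reply is that a pick from a well-shuffled pool is a valid random allocation, and that the plan has safeguards. The envelopes are sealed, so an opened one must be resealed, and a discarded one leaves a shortfall against 25 per arm. The circulating nurse makes the pick, while recruitment and consent belong to the investigators and study staff. The absence of numbers and a log is read from silence. The remark on surgeon preference concerns surgeons at the institution and does not say that the trial's own surgeons are among them. Preferences could also run in opposite directions and partly cancel.

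Most of this stands, and it limits the point. A reader might infer that redraws are likely, or that a bias of up to 2.5 points should be expected. The documents support neither: no redraw rate is given, and 2.5 needs both perfect foresight and one-way redraws. A reader might also infer that uneven arms within a site bias the comparison; step 5 shows that they do not.

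What does not stand is that the safeguards close the gap. Even numbered envelopes would not help if any one may be chosen, and a resealed envelope returned to the pool leaves the count intact. The pool's own count is also inconsistent, which weakens reconciliation by shortfall.

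A second objection concerns the remedy. Small blocks can be guessed by an unblinded team that also recruits. At a site of 25 with mixed blocks of 3 and 6, guessing the arm used least so far is right about 57% of the time, against 36% under the present pool and 33% by chance. That stands and shapes the fix.

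**Conclusion.** The concern holds as a weakness in allocation concealment that is cheap to remove. It does not show that the trial's comparison is biased. As written, a redraw could be neither detected nor ruled out. Its effect is unknown: at most 0.8-2.5 EAT-10 points under the one-way redraw illustration with q of 10-30%, and about 0.2-1.3 points if prognosis correlates 0.3-0.5 with outcome. All of these rest on assumed redraw rates.

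The plan also leaves unsaid how one pool reaches several sites, so balance within site is not ensured. At an assumed site of 25, a gap of 5 or more occurs 36% of the time. The cost is precision only, and a site term in the analysis would recover much of it. The undetectable redraw is the main point; site balance is secondary.

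**What to change.** Replace the shuffle-and-pick text in Section 5.0 with the following:
- A computer-generated list for each site, prepared by someone outside the enrolling and operating teams.
- Randomly varied, larger blocks (for example 6 and 9), with sizes not disclosed to sites. A part-filled block of 9 can hold three of one arm and none of another, so the gap within a site never exceeds 3.
- Opaque, sequentially numbered envelopes held at each site and opened strictly in order, only after consent, with subject number, date and time written on the envelope before opening.
- A log reconciled against the list at study end.

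In Section 6.0, include site as a factor in the EAT-10 comparison. In the same edit, reconcile the envelope count (85 or 75) in the synopsis and Sections 5.0 and 6.0.

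The cost is protocol wording and a few hours of preparation; no visits or treatments change. There are two downsides. Overall totals are no longer fixed at exactly 25 per arm. Blocks also remain partly predictable: repeating the guessing rule in 5,000 simulated sites of 25, with block size 6 or 9 equally likely, gives about 53% correct, so block size alone helps only a little. Keeping the sizes undisclosed and opening only after consent add protection. Releasing each assignment centrally after consent would also remove the possibility of handling envelopes out of order.

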2.0 OBJECTIVES

- To determine if the use of steroids decreases the incidence of dysphasia after anterior cervical discectomy and fusion (ACDF).
- If steroids are useful, determine which method of steroid administration is most efficacious (IV versus local application).
- We hypothesize that local application of steroids in ACDF surgery will lead to a decreased incidence of dysphagia, in the postoperative period as compared to intravenous steroids or a control group.
- To evaluate the incidence of dysphonia, as measured by the Voice Handicap Index (VHI-10), as well as other validated outcome measures (NDI, VAS, EQ-5D).

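### The schedule secures a preoperative value only for EAT-10 and Bazaz; VHI-10, NDI, VAS and EQ-5D have no stated time points, and the analysis plans no baseline adjustment

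*Combined protocol and SAP*

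**What the plan says.** Section 5.0 first names the primary outcome: "The primary outcome measure is the incidence of dysphagia as measured by Eating Assessment Tool (EAT-10) and the Bazaz score". The schedule follows directly: "The patients will prospectively fill out these surveys preoperatively, post-operative day 1, week 2, week 6, month 3, month 6, and 1 year". That sentence closes by tying the dates to swallowing: "1 year as a measure of dysphagia".

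The secondary instruments come in a later paragraph of section 5.0, which lists dysphonia by VHI-10, then NDI, VAS and EQ-5D, with no dates. The only text on when or where they are given is that the questionnaires "will be administered in the hospital, during the post-operative clinic visits with the surgeon, or over the phone". The paragraph ends with a clinician rating of dysphonia on four grades: "The surgeons will also listen to the patient's voice at these different time points".

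Section 2.0 states the aim as "To evaluate the incidence of dysphonia, as measured by the Voice Handicap Index (VHI-10), as well as other validated outcome measures". It gives neither timing nor a case definition.

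Section 6.0 compares EAT-10, VHI and EQ-5D scores by t-test (printed as T score) or ANOVA, and subjective findings by chi-square. It mentions no change from baseline and no adjustment for baseline, and it does not name NDI or VAS.

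Section 4.0 allows recruitment in clinic or "prior to their ACDF surgery in the pre-operative hold area", and makes each site responsible for its own data collection. The Data Collection Form in the appendices holds four complications and no questionnaire scores, so it does not settle the timing.

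**The concern.** A site can follow section 5.0 to the letter and give the first VHI-10, NDI, VAS and EQ-5D after surgery. Another site can read the same text as requiring them beforehand. A preoperative score that was not taken cannot be collected later. The window can also be short, since a patient may be recruited in the hold area and the envelope is drawn before the operation starts.

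Two things are at stake. First, incidence means new cases. Without a preoperative voice assessment, a post-operative voice complaint cannot be sorted into new or pre-existing, and the dysphonia objective becomes a comparison of prevalence. Second, patients with radiculopathy and patients with myelopathy will enter with differing disability, pain and health status. Without baseline scores, the trial cannot report change, cannot check for chance imbalance in arms of 25, and cannot use the baseline to sharpen the comparison.

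**Working it through.** **The plan's own figure.** The plan gives no number on this point. Its one calculated figure, power 0.92 with 25 per group and SD 12.7 (section 6.0), concerns EAT-10. It states no difference to detect, so it can only be solved backwards: 12.7 × √(2/25) × (1.960 + 1.405) = 12.1 points (two-sided 0.05, two groups, normal approximation). It says nothing about the secondary outcomes, and nothing below depends on it.

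**Reading the schedule (section 5.0)**

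| Measure | Dated schedule | Preoperative value |
|---|---|---|
| EAT-10, Bazaz | Yes, seven time points | Stated |
| VHI-10, NDI, VAS, EQ-5D | None; settings only | Not stated |
| Surgeon's voice rating | Refers back to time points | Depends on which time points are meant |

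**Effect on the incidence of dysphonia.** Let q be the fraction of patients, equal in both arms, with dysphonia before surgery that persists, and p₁ and p₂ the true new-onset rates. Without a baseline the observed rate is q + (1 - q)p, so the observed difference is (1 - q)(p₁ - p₂).

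The documents give neither q nor p. For illustration, assume p₁ = 40% and p₂ = 10%, two-sided 0.05, 25 per arm, normal approximation with pooled variance under the null:

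| q (assumed) | Observed rates | Difference | Power, all patients | Power, incident cases only, 25(1 - q) per arm |
|---|---|---|---|---|
| 0% | 40% v 10% | 30 points | 0.70 | 0.70 |
| 10% | 46% v 19% | 27 points | 0.53 | 0.65 (22.5 per arm) |
| 20% | 52% v 28% | 24 points | 0.41 | 0.60 (20 per arm) |

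The last column is the fair comparator, because patients with preoperative dysphonia leave the denominator once they are identified. Example for q = 20%: the standard error under the null is √(0.25 × 0.75 × 2/20) = 0.137 and under the alternative √((0.24 + 0.09)/20) = 0.128. Then z = (0.30 - 1.96 × 0.137)/0.128 ≈ 0.25, and power is about 0.60. On these assumptions, knowing the preoperative state gains 0.12 of power at q = 10% and 0.19 at q = 20%.

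**Effect on the scores.** With baseline correlation r (assumed), ANCOVA leaves a fraction 1 - r² of the variance. The equivalent increase in sample size is 1/(1 - r²) - 1. The detectable difference at 80% power, two-sided 0.05 and 25 per arm is √(1 - r²) × √(2/25) × (1.960 + 0.842) SD.

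| r (assumed) | Variance left | Variance saved | Equivalent extra patients | Detectable difference |
|---|---|---|---|---|
| 0, or no adjustment | 1.00 | 0% | 0% | 0.79 SD |
| 0.3 | 0.91 | 9% | 10% | 0.76 SD |
| 0.5 | 0.75 | 25% | 33% | 0.69 SD |
| 0.7 | 0.51 | 49% | 96% | 0.57 SD |

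Both steps are needed for this gain: a baseline score and an analysis that uses it. Section 6.0 as written would not obtain it even with every baseline in hand.

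**The case against.** The strongest reply is that silence is not absence. The hospital setting is not restricted to the period after surgery; only the clinic visits are. The sentence on settings speaks of the questionnaires in general, so it may cover EAT-10 and Bazaz, which are expressly given before surgery, and then it cannot exclude preoperative use. The voice-rating sentence refers back to a set of time points, and the only full list in the section begins preoperatively. On that reading dysphonia already has a preoperative grade from the surgeon, and the questionnaires may share the same dates. This stands. A reader might infer that the secondary outcomes have no baseline at all; the documents do not support that. They leave the question open, both before and after surgery.

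A second reply is that randomisation protects the comparison of post-operative scores. This also stands: a missing baseline costs precision, change scores and a check of balance, not validity. The same holds for post-operative dysphonia prevalence, which is a valid randomised contrast but not the incidence that section 2.0 names.

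A third reply is that the correlations and the values of q come from outside the documents. That is so. The 96% figure is the top of an assumed range, for secondary outcomes, and should not be read as a shortfall in the trial's sample size.

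What the replies do not remove is that the text can be followed in two ways by sites that each collect their own data, and one of those ways loses a value for good.

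**Conclusion.** The point holds as a gap in specification with a cheap remedy. Section 5.0 does not secure a preoperative VHI-10, NDI, VAS or EQ-5D, gives these instruments no time points at all, and leaves the timing of the surgeon's voice rating ambiguous. Section 6.0 plans no baseline adjustment.

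The clearest consequence is for the incidence of dysphonia, where the difference between arms shrinks by the factor (1 - q). This assumes that q is the same in both arms and that the preoperative problem persists. For the scores the loss is 9% to 49% of variance over assumed correlations of 0.3 to 0.7, and it arises from the schedule and the analysis together.

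The documents do not support two stronger conclusions: that these outcomes certainly lack a baseline, or that the post-operative comparisons are invalid. The primary instruments have an explicit preoperative assessment and are untouched. The change is worth making for secondary outcomes; it does not threaten the trial's main comparison.

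**What to change.** **Section 5.0.** State that VHI-10, NDI, VAS, EQ-5D and the surgeon's voice rating are collected preoperatively, after consent and before the envelope is drawn, and then at the same post-operative times as EAT-10 and Bazaz. A short table of instrument by time point would do this.

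**Section 6.0.** Compare VHI-10, NDI, VAS and EQ-5D scores by ANCOVA adjusted for the preoperative value, in place of the unadjusted t-test or ANOVA. Define incident dysphonia as present post-operatively in a patient without it preoperatively, using either a pre-specified VHI-10 cut-off or the surgeon's grade, chosen in advance. The documents give no cut-off, so the sponsor must supply and justify one if VHI-10 is used. Report post-operative prevalence in all randomised patients alongside.

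**Cost.** A few sentences and no extra visit, because EAT-10 and Bazaz are already completed before surgery. The patient's burden is at most about 20 minutes, the protocol's own estimate for the questionnaires; this will be felt most by patients recruited in the hold area. The incidence analysis loses patients with preoperative dysphonia: at an assumed q of 10% to 20%, 25 per arm becomes about 22.5 to 20. The prevalence report keeps everyone in view.

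### Surgeons who very likely know the arm grade dysphonia; the plan does not say whether that grade is tested, or keep questionnaires clear of the visit with the surgeon

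*Combined protocol and SAP*

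**What the plan says.** **Blinding.** Section 5.0 describes the trial "as part of a single blind, randomized controlled study" and states "Subjects will be blinded to the treatment arm". No other role is said to be blinded anywhere in the document.

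**When the arm becomes known.** "The circulating nurse in the OR will at random choose one envelop prior to the start of the operative procedure". The local treatment is "40mg of triamcinolone on gel foam sponge dabbed on the anterior cervical plate". The control arm is described as "group I (control group, no steroid", with no sponge mentioned. The intravenous arm also has a gel foam sponge on the plate.

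**Dysphonia.** Sections 2.0 and 5.0 both name VHI-10 as the measure. Section 5.0 adds that at the follow-up time points the surgeons listen to the voice and "comment on dysphonia as being absent, mild, moderate, or severe". It gives no grading criteria and no masked rater.

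**Questionnaires.** Patients fill out EAT-10 and Bazaz (the primary outcome) themselves. Questionnaires may be given in the hospital, "during the post-operative clinic visits with the surgeon, or over the phone". The plan does not say who gives them, or whether they come before or after the consultation.

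**Analysis.** Section 6.0 assigns a t-test or ANOVA to EAT-10, VHI and EQ-5D, and "Chi square for subjective findings", with the significance level at 0.05. It does not list what counts as a subjective finding.

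**The concern.** A four-level voice grade without criteria is a judgement. If the grader knows the arm and expects steroids to help, borderline patients can be graded more kindly in one arm or more harshly in another. Section 2.0 states such an expectation, though for dysphagia. A difference between arms can then appear with no true effect. If the grade is tested at 0.05, it could be reported as a steroid benefit on voice.

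The second route is weaker but touches more important outcomes. EAT-10, Bazaz and VHI-10 are self-reports, so their protection rests on the patient not knowing the arm. Completing them at a visit with someone who knows the arm, after or during a conversation about the operation, gives an opening for cueing or accidental disclosure. Subject blinding is the only blinding the trial states, and the plan does nothing at the visit to preserve it.

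**Working it through.** **Step 1: does the surgeon know the arm?** The document does not say so directly. Three facts in Section 5.0 make it very likely: only subjects are blinded, the envelope is drawn in the operating room before the procedure, and the local steroid is placed in the operative field. Two details limit the inference. The text says the surgeons grade the voice, not that each patient's own operating surgeon does. It also does not say who gives the intravenous drug.

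**Step 2: is the surgeon's grade tested?** Undetermined. A four-category grade fits a chi-square test. So does Bazaz: Section 1.0 calls it subjective, and it is missing from the t-test/ANOVA list in Section 6.0.

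**Step 3: how large could the bias be if the grade is tested?** The plan has no figure on this to reproduce; its stated power of 0.92 concerns EAT-10. The following is an illustration.

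- From the document: 25 per arm, chi-square test, significance level 0.05.
- Assumed: no true effect; true grades absent/mild/moderate/severe = 40/30/20/10% in every arm; a fraction q of grades moved one step, with q = 10%, 20% or 30%.

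Recorded grade probabilities after a shift, with the end categories unable to move further:

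| Grade | Shifted better | Shifted worse |
|---|---|---|
| Absent | 0.40 + 0.30q | 0.40 − 0.40q |
| Mild | 0.30 − 0.30q + 0.20q = 0.30 − 0.10q | 0.30 − 0.30q + 0.40q = 0.30 + 0.10q |
| Moderate | 0.20 − 0.20q + 0.10q = 0.20 − 0.10q | 0.20 − 0.20q + 0.30q = 0.20 + 0.10q |
| Severe | 0.10 − 0.10q | 0.10 + 0.20q |

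At q = 30% this gives 49/27/17/7% for an arm shifted better and 28/33/23/16% for an arm shifted worse.

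The test is Pearson chi-square on a 2 × 4 table, with (2 − 1)(4 − 1) = 3 degrees of freedom. Share of simulated trials with p < 0.05 (200,000 per setting):

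| Shift | q = 0 | q = 10% | q = 20% | q = 30% |
|---|---|---|---|---|
| Steroid arm better, control unshifted | 4.5% | 4.8% | 5.6% | 7.0% |
| Control arm worse, steroid unshifted | 4.6% | 5.3% | 7.4% | 10.7% |
| Steroid better and control worse | 4.6% | 6.3% | 12.1% | 23.8% |

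With no shift the rate is just under 5%, because some expected counts are small (25 × 0.10 = 2.5 severe grades per arm).

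**Three arms of 25.** With only the local arm favoured, the rates are 4.9%, 5.6% and 6.9% for q = 10%, 20% and 30%. With both steroid arms favoured and control shifted worse, they are 6.2%, 11.6% and 23.2%. The range therefore does not come from using two arms.

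**Step 4: the patient questionnaires.** No comparable calculation is possible. The document gives nothing from which to judge how often a patient would be cued or told the arm, and any effect would pass through the patient's own answer.

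**The case against.** The strongest case against is that this is a declared single-blind design whose outcomes are already protected. VHI-10 is the named dysphonia measure, blinded patients answer it and the primary questionnaires, and the surgeon's grade is only an added comment. Most of that stands, and it rules out three stronger readings that a reader might infer.

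- **That the plan tests the surgeon's grade at 0.05.** Section 6.0 does not say so; the undefined phrase may mean Bazaz. If the grade is not tested, the false-positive rates above do not apply to anything the plan does.
- **That EAT-10 and Bazaz are exposed in the same way as the grade.** They are not. Patients complete them, and a visit with the surgeon need not mean that the surgeon hands out the form or is in the room. Hospital and phone completion are also allowed.
- **That false positives would reach 24%.** That figure needs 30% of grades moved, in opposite directions in the two arms. With only the steroid arm favoured, the same q gives about 7%. No source in the document supports any value of q or the grade distribution.

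It is also fair to say that no staff are identified as unaware of the allocation. The staff who recruit may also collect data and review charts, so keeping phone callers unaware cannot be assumed to be free.

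The objection does not remove the gap. The plan has an unmasked subjective grade, an analysis clause wide enough to include it, and no rule on who gives the questionnaires or when.

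**Conclusion.** The concern holds in a limited form. Direct detection bias falls on one additional secondary assessment, the surgeon's voice grade, and matters for inference only if Section 6.0 is read to include it. In that case the two-arm false-positive rate runs from about 5–7% (steroid arm favoured) to about 6–24% (arms shifted in opposite directions) as q goes from 10% to 30%. That range rests entirely on the assumed grade distribution and values of q. For EAT-10, Bazaz and VHI-10 the risk is indirect and unquantified, and it does not show that the primary comparison is biased. That the surgeon knows the arm is a strong inference rather than a statement in the document. The change is worth making because every outcome concerned is subjective and the remedy is cheap.

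**What to change.** 1. **Section 6.0.** State that dysphonia is tested on VHI-10 only. List the variables that the chi-square clause covers, without the surgeon's grade. Report that grade descriptively by arm, labelled as unblinded.
2. **Section 5.0.** State that patients complete EAT-10, Bazaz and VHI-10 themselves, before they see the surgeon at each visit. Where a questionnaire is done by phone, have existing study staff who have not been told the allocation make the call, where feasible.

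**Cost.** Protocol wording, a fixed order at the visit, and minor control over which staff can see the allocation. No new rater or extra visit is needed. The surgeon's grade can no longer support a claim about voice, which is a small loss because an unblinded grade would be weak evidence in any case.
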